8.2.2. Definition of Serious Adverse Events

An SAE is an untoward medical occurrence or effect at any dose, regardless of whether it is considered to be related to the study intervention, which results in one of the following:

- Results in death. This includes all deaths on treatment or within 6 months after last study intervention administration, including deaths due to disease progression. Any death occurring later than 6 months following the last dose need not be reported as an SAE unless it is a result of an event that started within the period covered by the on-study definition. The reported AE should be the event that caused the death.
In addition, any AE resulting in death that occurs post the AE reporting period and that the investigator assesses as possibly related to the study intervention should also be reported as serious.

- Is life-threatening. This refers to an event in which the subject was at risk of death at the time of the event. It does not include an event that, had it occurred in a more severe form, hypothetically might have caused death.
- Requires hospitalization or prolongation of existing hospitalization (excluding hospitalizations for administration of the study intervention, procedures required by the study protocol, or treatment-related diagnostic procedures; other planned hospitalizations; or hospitalizations related only to progression of disease). Emergency room visits that do not require admission to the hospital do not fall into this category, but the event may still be serious due to another seriousness criterion.
- Results in persistent or significant disability or incapacity or substantial disruption of the ability to conduct normal life functions.
- Any other medically important event that the investigator or PTC judges to be serious or which is defined as serious by the regulatory agency in the local country. These are AEs that might not be immediately life-threatening or result in death or hospitalization but might jeopardize the subject or might require intervention to prevent one of the other outcomes listed above. Medical judgment should be exercised in deciding whether an AE is serious based on the above definition. Examples of such events are intensive treatment in an emergency room or at home for allergic bronchospasm, blood dyscrasias or convulsions that do not result in hospitalization, or development of drug dependency or drug abuse.

A pregnancy resulting in spontaneous abortion, stillbirth, neonatal death, or congenital anomaly (including that in an aborted fetus). Note: Hospitalization for social circumstances without any other accompanying SAE should not be reported as an SAE.

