8.2. Adverse Events, Serious Adverse Events, and Other Safety Reporting

8.2.1. Definition of Adverse Events

An AE is any untoward medical occurrence associated with the use of a study intervention in humans, whether or not it is considered related to the study intervention. An AE can therefore be any unfavorable and unintended sign (for example, an abnormal laboratory finding), symptom, or disease in a study subject who is administered with study intervention in this study.

For this protocol, untoward medical occurrences that meet and do NOT meet the criteria of an AE include the following:

Events Meeting the AE Definition

- All AEs during the course of treatment with study intervention
- All AEs resulting from medication misuse, abuse, withdrawal, or overdose of study drug
- All AEs resulting from medication errors, such as dispensing or administration error outside of what is described in the protocol
- Apparent unrelated illnesses, including worsening of a preexisting illness
- Injury or accidents. Note that if a medical condition is known to have caused the injury or accident (a fall secondary to dizziness), the medical condition (dizziness) and the accident (fall) should be reported as 2 separate AEs. The outcome of the accident (hip fracture secondary to the fall) should be recorded in source documents.

- Abnormalities in physiological testing or physical examination findings that require clinical intervention or further investigation (beyond ordering a repeat [confirmatory] test)
- Laboratory or ECG abnormalities that require clinical intervention or further investigation (beyond ordering a repeat [confirmatory] test) unless they are associated with an already reported clinical event

Events NOT Meeting the AE Definition

- Laboratory abnormalities associated with a clinical event should be captured in the source documents. Laboratory abnormalities not requiring clinical intervention or further investigation will be captured as part of overall laboratory monitoring and should not be reported as AEs.
- The disease/disorder being studied or expected progression, signs, or symptoms of the disease/disorder being studied, unless more severe than expected for the subject's condition (see Section 8.2.10).
- Preexisting condition (eg, allergic rhinitis) must be noted on the appropriate eCRF for Screening but should not be reported as an AE unless the condition worsens, or the episodes increase in frequency during the AE reporting period.

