- Diagnostic and therapeutic noninvasive and invasive procedures, such as surgery, should not be reported as AEs, unless the medical condition for which the procedure was performed meets the definition of an AE. For example, an acute appendicitis that occurs during the treatment with study intervention should be reported as the AE, and the resulting appendectomy should be recorded in the source documents and eCRF. If a surgical procedure was planned prior to entry into the study, and the surgery is not performed because of a worsening of a baseline condition, this should not be reported as an AE. Note that, as described in Section 8.2.2, any hospitalization occurring as the consequence of an AE during the study period should be reported as an SAE.

Each AE is to be classified as serious or nonserious by the investigator using medical and scientific judgment.

Treatment of AEs will be symptom-based and at the discretion of the investigator.

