8.2.3. Adverse Events Reporting

Adverse events will be reported by the subject.

The investigator and any qualified designees are responsible for detecting, documenting, and recording events that meet the definition of an AE or SAE and remain responsible to pursue and obtain adequate information both to determine the outcome and to assess whether the event meets the criteria for classification as an SAE or caused the subject to discontinue the study intervention (see Section 4.4).

Each subject will be questioned about the occurrence of AEs in a nonleading manner.

In addition, the investigator may be requested by PTC Pharmacovigilance Department to obtain specific follow-up information in an expedited fashion.

All AEs are to be recorded in the source documents and on the eCRF using concise medical terminology; whenever possible, terms contained in the Medical Dictionary for Regulatory Activities (MedDRA) should be employed. In addition, the following information should be recorded:

- Indication of whether the event is serious or nonserious (see Section 8.2.2)
- Relationship to study intervention (see Section 8.2.5)
- Severity of the event (see Section 8.2.5)

- Onset date
- Resolution date, or date of death
- Action taken
- Outcome of the event

Table 6 summarizes the investigator site requirements for recording AEs on the eCRF and for reporting SAEs and adverse events of special interest on the SAE Report Form to PTC Pharmacovigilance Department.

Table 6: Investigator Site Requirements for Recording/Reporting Adverse Events

Event	Recorded on the eCRF	Reported to PTC Pharmacovigilance Within 24 Hours of Awareness
Serious AE	All	All
Nonserious AE	All	None
AESI	Not applicable	Not applicable
Other, eg, exposure during pregnancy or breastfeeding	All (regardless of whether associated with an AE)	All (regardless of whether associated with an AE)

Abbreviations: AE, adverse event; AESI, adverse event of special interest; eCRF, electronic case report form

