8.2.4.1. Serious Adverse Event Reporting

All SAEs (both initial and follow-up) must be reported via the SAE Report Form to PTC Pharmacovigilance Department immediately, and under no circumstance should this exceed 24 hours from awareness. In addition, the AE portion of the eCRF must also be completed.

The SAE Report Form must be signed by the investigator; however, if the investigator is unable to sign at the time of the event or within 24 hours, the form should be signed by the clinical staff member reporting the SAE (eg, the study coordinator). The SAE Report Form must be faxed or emailed to the PTC Pharmacovigilance Department and to the site Institutional Review

Board (IRB)/Independent Ethics Committee (IEC) (if required by local regulations) within 24 hours. The investigator's signature must be obtained as soon as possible after the report is submitted, and the report revised if necessary and submitted to PTC Pharmacovigilance Department. The investigator will maintain a copy of the SAE Report Form on file at the study site.

Follow-up information to the SAE should be clearly documented as "follow-up" in the SAE Report Form and must also be faxed or emailed to the same party within the same timelines. All follow-up SAE Report Forms for the event must be signed by the investigator as per instructions above. Any source documents (eg, progress notes, nurses' notes, laboratory and diagnostic test results, discharge summaries) provided to PTC should be redacted so that the subject's name, address, and other personal identity information are obscured. Only the subject's study number and initials are to be provided (in regions where the provision of such information is permitted). The information in the AE portion of the eCRF and the SAE Report Form(s) must match or be reconciled. Where the same data are collected, the forms must be completed in a consistent manner. For example, the same AE term should be used on both forms.

The PTC Pharmacovigilance Department contact information for reporting SAEs is provided below. This information is also provided in the SAE Report Form.

PTC Pharmacovigilance Department
Email: [contact]
SAE Fax Line: [contact]

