8.2.5.2. Describing Adverse Event Relationship to Study Intervention

The investigator should provide an assessment of the relationship of the AE/SAE to the study intervention, and each occurrence of each AE/SAE as outlined in [Table 8](#). The investigator will use clinical judgment to determine the relationship.

The investigator will also consult the Investigator's Brochure in his/her assessment.

For each AE/SAE, the investigator must document in the medical notes that he/she has reviewed the AE/SAE and has provided an assessment of causality.

There may be situations in which an AE/SAE has occurred, and the investigator has minimal information to include in the initial SAE Report Form to PTC Pharmacovigilance Department. However, it is very important that the investigator always make an assessment of causality for every event before the initial transmission of the SAE Report Form to PTC Pharmacovigilance Department.

The investigator should decide whether, in his or her medical judgment, there is a reasonable possibility that the event may have been caused by the investigational product.

- If no valid reason exists for suggesting a relationship, then the AE should be classified as “unrelated.” If a relationship cannot be excluded but there is a clear alternate cause that is more likely to have caused the AE than study intervention, the AE should be considered “unlikely related.”
- If there is any valid reason, even if undetermined, for suspecting a possible cause-and-effect relationship between the investigational product and the occurrence of the AE, then the AE should be considered “possibly or probably related.”

If the relationship between the AE/SAE and the investigational product is determined to be “possible” or “probable,” the event will be considered to be related to the investigational product or the purposes of expedited regulatory reporting. An assessment of “unlikely related” will be considered unrelated for regulatory reporting purposes.

The investigator may change his/her opinion of causality in light of follow-up information and must send an SAE Follow-Up Report Form with the updated causality assessment.

The causality assessment is one of the criteria used when determining regulatory reporting requirements ([Table 8](#)).

Table 8: Relationship of Study Intervention to Adverse Event

Relationship	Description

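### The SAE hospitalization criterion (Protocol 8.2.2) excludes every admission due only to disease progression, including the worse-than-expected progression that 8.2.1 makes an adverse event

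*Protocol*

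**What the plan says.** Four parts of the protocol bear on an admission caused by Huntington's disease itself.

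- **8.2.1 (definition of an AE).** The disease under study and its expected course are not AEs, "unless more severe than expected for the subject's condition". The same section, referring to 8.2.2, notes that "any hospitalization occurring as the consequence of an AE during the study period should be reported as an SAE".
- **8.2.2 (definition of an SAE).** An event is serious or not "regardless of whether it is considered to be related to the study intervention". The hospitalization bullet then carries a parenthesis of exclusions, which ends with "other planned hospitalizations; or hospitalizations related only to progression of disease". The death bullet in the same list goes the other way: "This includes all deaths on treatment or within 6 months after last study intervention administration, including deaths due to disease progression".
- **8.2.3 and 8.2.4.1 (recording and reporting).** The seriousness field on the eCRF points the site to 8.2.2. All SAEs "must be reported via the SAE Report Form to PTC Pharmacovigilance Department immediately, and under no circumstance should this exceed 24 hours from awareness". Table 6 requires nonserious AEs to be recorded on the eCRF but asks for no 24-hour report.
- **8.2.10.1 (progression of underlying disease).** Progression beyond what is normally expected, or possibly caused by study drug or procedures, goes to pharmacovigilance within 24 hours, on condition that the seriousness criteria are met.

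SAP 6.1 tabulates treatment-emergent SAEs separately from all TEAEs.

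**The concern.** The protocol separates expected from worse-than-expected progression in 8.2.1, in 8.2.10.1 and again in 8.2.10.2 for abnormal findings. The hospitalization exclusion in 8.2.2 does not make that distinction. Read as written, it takes out the admissions that the other sections treat as adverse and reportable.

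Safety is a primary objective, and NfL, which the protocol describes as a marker of neuronal injury, is a safety endpoint. Neurological worsening faster than expected is therefore something the safety tables should show with its correct seriousness. At stake are prompt reporting of such an admission and its place in the serious-event counts.

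**Working it through.** No arithmetic beyond a count applies. The check puts one test case through each section.

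**Test case.** A subject is admitted solely because Huntington's disease has worsened faster than expected. The event is not life-threatening, causes no lasting disability, and neither the investigator nor the sponsor judges it medically important.

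| Step | Section | Result |
|---|---|---|
| 1. Is it an AE? | 8.2.1 | Yes: the progression is more severe than expected |
| 2. Does the admission make it an SAE? | 8.2.1, note on hospitalization | Yes: it is a hospitalization resulting from an AE |
| 3. Does it meet the hospitalization criterion? | 8.2.2, third bullet | No: it is related only to progression, and the exclusion has no limit to expected progression |
| 4. Does the special rule on progression settle it? | 8.2.10.1 | No: see below |

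**Step 4.** The 24-hour report depends on the event meeting the seriousness criteria, which are those of 8.2.2, so the rule leads back to step 3. The sentence can also be parsed so that this condition attaches only to the causality trigger. The prompt report is then owed, but the event is still not classified as an SAE.

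**Which answer a site is likely to reach.** The note in step 2 presents itself as a restatement of 8.2.2, and 8.2.3 sends the site to 8.2.2 for the seriousness field. A site that follows both pointers ends at step 3 and codes the event nonserious. That has two consequences:

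- no 24-hour report under Table 6;
- no entry in the treatment-emergent SAE tables of SAP 6.1.

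**Scope.** Section 8.2.2 lists six criteria: death, life-threatening event, hospitalization, disability, other medically important event, and specified pregnancy outcomes. One (hospitalization) excludes progression, one (death) expressly includes it, and the other 6 − 1 − 1 = 4 do not mention it. The gap therefore opens only when admission is the sole serious feature.

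**Frequency.** The documents give no hospitalization rate, so no expected count can be derived. Subjects are ambulatory with a TFC of 11 to 13 at entry, which points to few such admissions over 12 months.

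**The case against.** **Section 8.2.2 governs, so there is no conflict.** It is true that 8.2.1 and 8.2.3 both direct the reader to 8.2.2. A reader might infer that the protocol leaves two rules of equal rank and that sites will split between them. The documents do not support that: the cross-references favor 8.2.2. But if 8.2.2 governs, its literal rule drops the admissions that 8.2.1 and 8.2.10.1 mean to capture. The objection changes the likely outcome from mixed coding to under-coding; it does not remove the problem.

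**The sections can be harmonized.** On this reading the 8.2.2 parenthesis covers ordinary progression and 8.2.10.1 the exceptional kind. That is probably what was intended. A site can reach it only by adding a word that 8.2.2 does not contain.

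**Other criteria will catch the event.** Often they will. Progression that needs admission may disrupt normal life enough to qualify as disability, and either the investigator or the sponsor may judge any event medically important. This is a real backstop and it narrows the gap. It is also discretionary, so it does not make the hospitalization rule correct.

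**Drug-caused worsening could escape expedited reporting.** A reader might infer this stronger claim. It is largely unsupported. An admission suspected to be drug-related is not related only to progression, so it falls outside the exclusion. One judged unlikely related "will be considered unrelated for regulatory reporting purposes" in any case. What remains is drug-accelerated progression that a site takes to be progression alone.

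**Conclusion.** The concern holds as a minor point, and the text is wrong as written. The hospitalization exclusion in 8.2.2 lacks the limit to expected progression that the surrounding sections apply. An admission for worse-than-expected progression with no other serious feature, and not judged medically important, is likely to be coded nonserious, to receive no 24-hour report under Table 6, and to be absent from the treatment-emergent SAE tables.

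This rests on sites following the cross-references to 8.2.2 and reading its parenthesis literally. The number of such events is assumed small but cannot be calculated.

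Three further inferences should not be drawn:

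- **That the events are lost.** They stay on the eCRF and, within the treatment-emergent window, in the TEAE tables. The DSMB examines accumulated safety data (Protocol 10.3).
- **That the arms are biased against each other.** The rule is the same in every arm and the study is double-blind, so no such bias is claimed. Blinding is not complete, however: SAP 2.2 refers to subjects unblinded because of a partial clinical hold.
- **That efficacy is affected.** No efficacy endpoint, estimand or efficacy analysis depends on this definition.

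**What to change.** **Protocol.** In the third bullet of 8.2.2, replace the last exclusion with: *hospitalizations related only to expected progression of disease (not more severe than expected and not suspected to be caused by study drug or procedures; see Section 8.2.10.1)*. Make the change at the next amendment, with the IRB/IEC approval that Section 12.1 requires. Sections 8.2.1, 8.2.2 and 8.2.10.1 then agree.

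**Data already collected.** Before database lock:

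1. List all admissions recorded as disease progression. Keep the listing blinded, except for subjects already unblinded by the partial clinical hold.
2. Query the investigator on seriousness for each one, since 8.2.1 gives that classification to the investigator.
3. Reconcile the eCRF with the SAE form, as 8.2.4.1 requires, so that any reclassified event enters the SAP 6.1 treatment-emergent SAE tables.

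**Cost.** One clause in an amendment, a short listing review, a few queries, and possibly a few more SAE reports. No new visits or assessments.

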8.2.3. Adverse Events Reporting

Adverse events will be reported by the subject.

The investigator and any qualified designees are responsible for detecting, documenting, and recording events that meet the definition of an AE or SAE and remain responsible to pursue and obtain adequate information both to determine the outcome and to assess whether the event meets the criteria for classification as an SAE or caused the subject to discontinue the study intervention (see Section 4.4).

Each subject will be questioned about the occurrence of AEs in a nonleading manner.

In addition, the investigator may be requested by PTC Pharmacovigilance Department to obtain specific follow-up information in an expedited fashion.

All AEs are to be recorded in the source documents and on the eCRF using concise medical terminology; whenever possible, terms contained in the Medical Dictionary for Regulatory Activities (MedDRA) should be employed. In addition, the following information should be recorded:

- Indication of whether the event is serious or nonserious (see Section 8.2.2)
- Relationship to study intervention (see Section 8.2.5)
- Severity of the event (see Section 8.2.5)

- Onset date
- Resolution date, or date of death
- Action taken
- Outcome of the event

Table 6 summarizes the investigator site requirements for recording AEs on the eCRF and for reporting SAEs and adverse events of special interest on the SAE Report Form to PTC Pharmacovigilance Department.

Table 6: Investigator Site Requirements for Recording/Reporting Adverse Events

Event	Recorded on the eCRF	Reported to PTC Pharmacovigilance Within 24 Hours of Awareness
Serious AE	All	All
Nonserious AE	All	None
AESI	Not applicable	Not applicable
Other, eg, exposure during pregnancy or breastfeeding	All (regardless of whether associated with an AE)	All (regardless of whether associated with an AE)

Abbreviations: AE, adverse event; AESI, adverse event of special interest; eCRF, electronic case report form

8.2.4. Time Period and Frequency for Collecting/Reporting Adverse Event Information

The AE (both serious and nonserious) collection and AE reporting period begins with the signing of the ICF and continues until 6 months after the last dose of study medication. All AEs during this time period must be recorded whether or not the event is considered drug related.

For subjects who are screen failures, the active collection period for AEs ends when screen failure status is determined. Any SAEs occurring during screening procedures should be reported, and the appropriate causality assessment (ie, “not related” to study intervention) section of the SAE Report Form must be completed.

If the subject withdraws from the study and also withdraws consent for the collection of future information, the active collection period for AEs ends when consent is withdrawn.

Investigators are not obligated to actively seek information on AEs or SAEs after conclusion of the study participation. However, if the investigator learns of any SAE, including a death, at any time after a subject has been discharged from the study, and he/she considers the event to be reasonably related to the study intervention, the investigator must promptly notify PTC Pharmacovigilance Department via the SAE Report Form.

